iUPD with no change OR decrease from last TP	iUPD with no change OR decrease from last TP	Yes	NA	NLs confirms iCPD if NLs were previously identified and increase in size (≥ 5 mm in SOM for NLT or any increase for NLNT) or number.
iSD	iUPD	No	iUPD	Remains iUPD unless iCPD confirmed based in further increase in size of NT disease (need not meet RECIST 1.1 criteria for unequivocal PD)
iUPD	Non-iCR/Non-iU PD	No	iUPD	Remains iUPD unless iCPD confirmed based on: o further increase in SOM of at least 5 mm, otherwise remains iUPD
iUPD	iUPD	No	iUPD	Remains iUPD unless iCPD confirmed based on further increase in: o previously identified T lesion iUPD SOM ≥ 5 mm and / or o NT lesion iUPD (prior assessment - need not be unequivocal PD)

Proprietary confidential information © 2021 Boehringer Ingelheim International GmbH or one or more of its affiliated companies

iUPD	iUPD	Yes	iUPD	Remains iUPD unless iCPD confirmed based on further increase in: 
 o previously identified T lesion iUPD ≥ 5 mm and / or o previously identified NT lesion iUPD (need not be unequivocal) and /or o size or number of new lesions previously identified
Non-iUPD/PD	Non-iUPD/PD	Yes	iUPD	Remains iUPD unless iCPD confirmed based on 
 o increase in size or number of new lesions previously identified
* Using RECIST 1.1 principles. If no PSPD occurs, RECIST 1.1 and iRECIST categories for CR, PR and SD would be the same. ** in any lesion category. *** previously identified in assessment immediately prior to this TP.				

All patients will have their iBOR from the start of study treatment until the end of treatment classified as outlined below.

Table 10.6: 2 iRECIST Best Overall Response (iBOR)

TPR1	TPR2	TPR3	TPR4	TPR5	iBOR
iCR	iCR	iCR, iPR, iUPD, NE	iUPD	iCPD	iCR
iUPD	iPR, iSD, NE	iCR	iCR	iCR, iPR, iSD, iUPD, NE	iCR
iUPD	iPR	iPR	iPR, iSD, iUPD, NE	iPR, iSD, iUPD, NE, iCPD	iPR
iUPD	iSD, NE	iPR	iPR	iPR, iSD, iUPD, NE	iPR
iUPD	iSD	iSD, iUPD, NE	iSD, iUPD, iCPD, NE	iSD, iUPD, iCPD, NE	iSD
iUPD	iCPD	Anything	Anything	Anything	iCPD
iUPD	iUPD	iCPD	Anything	Anything	iCPD
iUPD	NE	NE	NE	NE	iUPD

- NE = not evaluable that cycle.
- Designation “T” for BOR can be used to indicate prior iUPD to aid in data interpretation.
- For patients with non-target disease only at baseline, only CR or non-CR/non-PD can be

assigned at each TPR but is not shown in the table for ease of presentation.

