Scenario 4 and 5 represents that the case that 1 DLT is observed in the first 6 patients at the starting dose of 240 mg, and the next dose level is kept the same where 0 or 1 DLT occurred.

Scenario 6 and 7 represents that the case that 2 DLTs are observed in the first 6 patients at the starting dose of 240 mg and the next dose level is different based on the SMC decision.

Table 10.5: 1 Hypothetical data scenarios

Scenario	Dose (mg)	# Patients	# DLT	Current Dose : P(OD)	Next recommended dose (mg)	Next dose:		
						P(UD)	P(TD)	P(OD)
1	240	6	0	0.005	240	0.926	0.069	0.005
2	240	6	1	0.043	240	0.686	0.271	0.043
3	240	6	2	0.173	240	0.367	0.460	0.173
4	240	6	1					
	240	3	0	0.015	240	0.795	0.195	0.015
5	240	6	1					
	240	3	1	0.071	240	0.519	0.410	0.071
6	240	6	2					
	80	3	0	0.010	240	0.452	0.435	0.112
7	240	6	2					
	240	3	1	0.207	240	0.255	0.537	0.207

Operating characteristics

Operating characteristics are a way to assess the long-run behaviour of a model by illustrating the precision of the design in estimating the MTD. Under an assumed true dose-toxicity curve, metrics such as the probability of recommending a dose with true DLT rate in the target interval can be approximated via simulation. Table 10.5: 2 describes 4 assumed true dose-toxicity scenarios which were used to assess the operating characteristics of the model. The scenario setting was referred to 1381-0001 trial assumptions. These scenarios reflect a wide range of possible cases as follows:

- Scenario 1: aligned with prior means
- Scenario 2: low-toxicity scenario
- Scenario 3: high-toxicity scenario
- Scenario 4: low-toxicity followed by high-toxicity

Table 10.5: 2 Assumed true dose-toxicity scenarios

Scenario		Dose (mg)		
		80	240	400
1: Prior	P(DLT)	0.096	0.164	0.257
2: Low Tox		0.001	0.009	0.028
3: High Tox		0.100	0.200	0.300

4: Low-High		0.001	0.180	0.360
-------------	--	-------	-------	-------

For each of these scenarios, 1000 trials were simulated. The each cohort consisted of 3 patients and the MTD was considered reached if at least 6 patients have been evaluated at a dose level which is the model's recommendation for the next dose cohort and for which the posterior probability of targeted toxicity was at least 50%.

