It was then assessed how often a dose was declared as MTD with true DLT rate in the under-, targeted-, or over-dose range. Furthermore, the average, minimum and maximum number of patients per trial and the average number of DLTs per trial are reported. Results are shown in Table 10.5: 3.

Table 10.5: 3 Simulated operating characteristics

Scenario	% of trials declaring a MTD with true DLT rate in				# Patients	# DLTs
	Underdose	Target dose	Overdose	Stopped Before MTD		
1: Prior	44.2	53.4	0	2.4	10.1 (3-33)	1.59 (1-6)
2: Low Tox	76.9	0	0	23.1	34.8 (6-60)	0.8 (0-2)
3: High Tox	50.7	45.5	0	3.8	9.56 (3-33)	1.67 (1-6)
4: Low-High	48.9	42.3	8.0	0.8	9.78 (3-30)	1.39 (1-6)

In scenario 1 (Prior), which reflects the case that the true dose-toxicity is aligned with prior means, 53.4% of the simulated trials that have found a MTD declared the MTD with true toxicity rate in the target interval. Few simulated trials (2.4%) have been stopped before declaring a MTD.

In scenario 2 (Low-toxicity scenario), since none of the assumed true dose-toxicity scenarios were beyond 16%, 76.9% of the simulated trials declared a dose as MTD with true DLT rate in the under dose range. 23.1% of the trials stopped before MTD was reached.

In scenario 3 (High-toxicity scenario) illustrate a behaviour similar to scenario 1 because of the similar setting dose toxicity scenarios.

In scenario 4 (Low-High scenario) shows 42.3% of the simulated trials declared a dose as MTD with true DLT rate in the targeted dose range. 8.0% of the simulated trials declared a dose as MTD in the overdose range. This is because the assumed true dose-toxicity rate at 400 mg was above 33%.

The mean patients numbers range from 9 to 10 patients except for scenario 2 (Low-toxicity scenario). The mean patients number was around 35 patients at scenario 2. But in case low toxicity and no safety concern at RD level (i.e. 240 mg), the SMC may recommend stopping the dose finding phase.

In summary, the considered data scenarios show a reasonable behaviour of the model and the operating characteristics demonstrate a good precision of MTD determination.

Part II

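### Table 10.5:3 does not follow from the MTD rule that Protocol Section 10.5 says was simulated: far more trials declare an MTD than its own DLT column allows, and the 8.0% overdose rate is not reproduced

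*Protocol*

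**What the plan says.** Protocol Section 10.5 sets out the Part I simulation: "For each of these scenarios, 1000 trials were simulated", and "The each cohort consisted of 3 patients". An MTD counted as reached when "at least 6 patients have been evaluated at a dose level which is the model's recommendation for the next dose cohort", joined by AND to the condition that the "posterior probability of targeted toxicity was at least 50" per cent. Sections 4.1.6 and 7.1.1 give similar criteria for the trial itself but join them with OR.

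Table 10.5:3 reports the results. For scenario 2 (low toxicity) the text says that "76.9% of the simulated trials declared a dose as MTD with true DLT rate in the under dose range". For scenario 4 (low, then high) it says that "8.0% of the simulated trials declared a dose as MTD in the overdose range". It calls 53.4% in scenario 1 a share of the trials that found an MTD. The Part II text does the same with 69.3%. The section ends Part I by saying that "the operating characteristics demonstrate a good precision of MTD determination", and ends Part II with the same claim.

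Table 10.5:1 gives posterior probabilities for example data at 240 mg. The target-interval probability is 0.271 after 1 DLT in 6 patients, 0.460 after 2/6, 0.410 after 2/9 and 0.537 after 3/9.

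**The concern.** Tables 10.5:1 and 10.5:3 pull in opposite directions. At 240 mg the examples with 0, 1 or 2 DLTs all stay below 0.50. Yet Table 10.5:3 has 77-99% of trials declaring an MTD on a mean of 0.8 to 1.67 DLTs, and no scenario 2 trial with more than 2.

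The MTD is a primary endpoint of Parts I and II. These tables are the simulation evidence offered for the design's precision, and SAP Section 7.4 relies on the same model for the MTD analysis. If the figures do not describe the stated design, the precision claim has no support, and the chance of declaring an over-toxic dose is understated.

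**Working it through.** **Inputs.** Model, reference dose (400 mg) and overdose limit: Section 7.1.1. Prior: Table 7.1.1:2. True rates: Tables 10.5:2 and 10.5:5. Printed results: Tables 10.5:3 and 10.5:6.

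**1. Reproduce the plan's posterior.** The two-parameter model on a fine grid gives these target probabilities at 240 mg, against Table 10.5:1:

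| Data | Recomputed | Printed |
|---|---|---|
| 0/6 | 0.075 | 0.069 |
| 1/6 | 0.276 | 0.271 |
| 2/6 | 0.452 | 0.460 |
| 2/9 | 0.410 | 0.410 |
| 3/9 | 0.526 | 0.537 |

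Agreement is within about 0.02.

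**2. Fewest DLTs that meet the rule.** I enumerated data in multiples of 3 patients over 80, 240 and 400 mg, up to 27 patients in total. The dose had to hold at least 6 patients and satisfy the overdose limit. Maximum target probability:

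| Total DLTs | 80 mg | 240 mg | 400 mg |
|---|---|---|---|
| 1 | 0.18 | 0.28 | 0.42 |
| 2 | 0.39 | 0.48 | 0.51 |

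The 2-DLT maxima occur at 6 to 9 patients in total, so the limit of 27 does not drive them. With 2 DLTs, 400 mg just passes: 0/3 at 240 mg then 2/6 at 400 mg gives 0.51, with overdose probability 0.22. So the rule needs at least 2 DLTs, and at least 3 for an MTD of 80 or 240 mg.

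**3. Bounds from the DLT column.** In scenarios 1, 3 and 4 every trial has at least 1 DLT, so the share with 2 or more is at most mean - 1, and the share with 3 or more is at most (mean - 1)/2. In scenario 2 the minimum is 0, so the share with 2 or more is at most mean/2. These are exact for the simulated trials and carry no sampling error. The share declaring is the sum of the underdose, target and overdose columns.

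| Scenario | Mean DLTs (range) | At most with 2 or more | Declaring an MTD |
|---|---|---|---|
| 1 | 1.59 (1-6) | 59% | 44.2 + 53.4 = 97.6% |
| 2 | 0.8 (0-2) | 0.8/2 = 40% | 76.9% |
| 3 | 1.67 (1-6) | 67% | 50.7 + 45.5 = 96.2% |
| 4 | 1.39 (1-6) | 39% | 48.9 + 42.3 + 8.0 = 99.2% |

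In scenarios 1, 3 and 4 only 80 mg has a true rate below 0.16, so every underdose declaration is 80 mg and needs 3 or more DLTs. At most 0.59/2 = 29.5%, 0.67/2 = 33.5% and 0.39/2 = 19.5% of trials can have that many. The underdose column alone shows 44.2%, 50.7% and 48.9%.

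**4. Re-simulation.** 4,000 trials per variant, varying start dose (80 or 240 mg), first cohort (3 or 6), maximum N, and the prior (printed, or tuned to Table 7.1.1:3).

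| Rule | Scenario 2 declaring | Scenario 4 overdose (400 mg) |
|---|---|---|
| AND, maximum 60 | 1.2-1.5% | 36-42% |
| AND, maximum 18-30 | 1.2-1.6% | 27-40% |
| OR | 100% | 25-35% |
| Printed | 76.9% | 8.0% |

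The Monte Carlo standard error of the printed 8.0% is sqrt(0.08 x 0.92/1000) = 0.9 percentage points, so noise does not explain the gap. Under the OR rule, scenario 2 stops after a mean of 9 to 12 patients (34.8 printed).

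**5. Table 10.5:6, without any model.** The mean number of DLTs must lie between mean patients times the lowest true rate and mean patients times the highest.

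- Scenario 1: lowest rate 0.146, so at least 27.41 x 0.146 = 4.0 DLTs. Printed: 1.24.
- Scenario 2: highest rate 0.160, so at most 11.97 x 0.160 = 1.92 DLTs. Printed: 2.161. The standard error is at most sqrt(11.97 x 0.16 x 0.84/1000) = 0.04, so the excess of about 0.25 is not noise.

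The printed ratios are 1.24/27.41 = 0.045 and 2.161/11.97 = 0.181. Each would fit the other scenario's rates, so an exchange of entries between the two rows is worth checking.

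**6. Denominators.** 53.4/97.6 = 54.7%, and 69.3/(14.0 + 69.3) = 83.2%. The printed 53.4% and 69.3% are shares of all trials.

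**The case against.** The strongest reply is that little depends on this table. Table 4.1.3:1 lists only 80 and 240 mg for Part I, so the scenario 4 overdose dose was not a listed level. The SMC decides doses and may stop at the recommended dose. Part I data already feed the July 2018 prior update (Table 7.1.2:1), so no Part I dose decision still waits on these simulations. All of this stands and limits the consequence. It does not make the printed figures right.

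A second reply is that the simulation's start dose, maximum N, first cohort size and dose-skipping rule are not stated, and that the printed prior does not reproduce Table 7.1.1:3 exactly (overdose probability at 80 mg 0.035 recomputed, 0.076 printed). This also stands. It is why the re-simulated overdose rate is a range and cannot serve as a replacement value. The bounds in step 3 depend on none of those settings except the prior. A prior tuned to Table 7.1.1:3 gives the same minimum numbers of DLTs.

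Three stronger readings are tempting but not supported:

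- A reader might infer from Table 10.5:1 that 3 DLTs are always needed, so that no scenario 2 trial could declare. At 400 mg, 2 DLTs narrowly suffice, so the scenario 2 limit is 40%, not zero.
- A reader might apply a minimum-DLT bound to scenarios 3 and 4 of Table 10.5:6. That needs the Part II reference doses, which are not printed. Only the model-free check in step 5 is safe.
- A reader might put the whole discrepancy down to AND against OR. Neither rule reproduces the table.

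**Conclusion.** The point holds. Table 10.5:3 is incompatible with the stated AND rule and the printed prior in all four scenarios: declarations exceed the attainable share by 38.6, 36.9, 29.2 and 60.2 percentage points. The scenario 4 overdose rate is roughly 25-42% over the settings tried, against 8.0% printed. Table 10.5:6 has impossible DLT means in scenarios 1 and 2.

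The Part I result assumes the Table 7.1.1:2 prior and the recommendation rule of Section 7.1.1. The Part II check assumes that only the four combinations in Table 10.5:5 were simulated. Even the lowest prior mean in Table 7.1.2:7 (0.092, at 240/4 mg) would give 27.41 x 0.092 = 2.5 DLTs in scenario 1.

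The documents do not show where the error arose, and nothing here shows that a dose decision was wrong. What fails is the evidence for the precision claim. As printed, Table 10.5:3 supports that claim weakly in any case, since 44-51% of trials in scenarios 1, 3 and 4 select an underdose.

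**What to change.** - Re-run Tables 10.5:3 and 10.5:6 under the MTD rule that the trial applies, after reconciling the AND wording of Section 10.5 with the OR wording of Sections 4.1.6 and 7.1.1.
- State the rule, prior, reference doses, start dose, first cohort size and maximum N used.
- Replace both tables and every percentage quoted from them, including the overdose and no-MTD rates. Before release, check that the DLT column is compatible with the declaration rule and with the assumed rates.
- Correct the denominators: on the present figures, 54.7% and 83.2% of trials declaring an MTD.
- Reword the two summary statements on precision to match the re-run.

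The cost is a short simulation run, two replacement tables and a few sentences. Some figures are likely to look less favourable, notably the scenario 4 overdose rate.

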As previously mentioned, significant improvement in checkpoint inhibitor effect has been achieved with checkpoint inhibitor combination therapy. The combination of nivolumab and ipilimumab, for example, has resulted in significant improvement in ORR, compared to checkpoint inhibitor monotherapy in patients with NSCLC and melanoma ([R16-5545](#), [R15-3696](#); [R16-5544](#)). Unfortunately, the improved efficacy of combined nivolumab and ipilimumab was associated with a significant increase in the rate and severity of AEs. Grade 3 and 4 AE rates of 53% to 55% were reported with the full-dose combination of nivolumab and ipilimumab in patients with melanoma ([R15-3696](#); [R16-5544](#)) and 33% to 37% with reduced dose and dosing frequency of the ipilimumab component in NSCLC compared to approximately 10% for nivolumab monotherapy in these populations ([R15-3696](#); [R16-5544](#)).

Treatment with BI 754091 and BI 754111 is anticipated to be associated with a similar pattern of AEs. Immune-related AE management guidance will be provided in the trial documentation. Infusion-related reactions have been reported with checkpoint-inhibitor treatments. These reactions occur infrequently and are typically managed based on symptoms using treatments ranging from histamine antagonists in mild cases to administration of epinephrine when symptoms of anaphylaxis are detected. Detailed irAE management guidelines are presented in Appendix [10.2](#).

Based on the pre-clinical data, as well as clinical data obtained with BI 754091 and other anti-PD-1 mAbs, the inhibitory effects of the combination of BI 754091 and BI 754111 may

Proprietary confidential information © 2021 Boehringer Ingelheim International GmbH or one or more of its affiliated companies

translate into a clinical benefit in cancer patients. The dose-escalation scheme is guided by a Bayesian Logistic Regression Model (BLRM) (de-escalation of dose is possible in case of insufficient tolerability of a dose level) and is designed to escalate the dose quickly and minimise the risk of safety issues.

In addition, dose levels which are higher than the ones investigated in preceding trials 1381-0001 and 1381-0002 will not be investigated in this trial.

Therefore, treatment with BI 754091 and BI 754111 may provide patients with clinical benefit at an acceptable risk.

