2.1.2 Primary endpoints

The primary endpoints of Part I (BI 754091 monotherapy dose-finding) are:

- Maximum tolerated dose (MTD) of BI 754091
- Number of patients experiencing dose limiting toxicities (DLTs) during the MTD evaluation period (first cycle of treatment)

The primary endpoints of Part II (combination dose finding) are:

- MTD of the BI 754091 plus BI 754111 combination
- Number of patients experiencing DLTs during the MTD evaluation period (first cycle of treatment)

The definition of MTD is described in Section [4.1.6](#). For definition of DLTs, refer to Section [4.1.5](#).

The primary endpoint of Part III (expansion) is:

- Objective response (OR) - confirmed complete response (CR) or partial response (PR) according to response evaluation criteria in solid tumours (RECIST) Version 1.1 ([R09-0262](#)) as assessed by the Investigator.

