4.1.2.2 Starting dose of BI 754111

BI 754111 will be tested at a starting dose of 400 mg to be administered via infusion q3w. In case of DLTs in 400 mg cohort, lower doses may also be explored.

The starting dose was selected based on the data obtained in 1381-0002 dose-escalation cohorts. By the end of June 2018, BI 754111 was administered at dose range from 4 mg to 600 mg in combination with BI 754091 240 mg. DLTs were not reported at any dose level and the MTD was not reached.

Table 4.1.2.2: 1 Number of evaluable patients and DLTs in trial 1381-0002 (as of Jun 2018)

Dose level	BI 754091 dose	BI 754111 dose	Number of evaluable patients	Number of DLTs
1	240 mg	4 mg	3	0
2	240 mg	20 mg	9	0
3	240 mg	80 mg	9	0
4	240 mg	200 mg	9	0
5	240 mg	400 mg	9	0
6	240 mg	600 mg	9	0
Total	-	-	48	0

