7.7 DETERMINATION OF SAMPLE SIZE

7.7.1 Determination of sample size for Part I and Part II

For Part I and Part II, no formal statistical power calculations of sample size were performed. A minimum of 6 and up to approximately 12 patients for Part I are expected. A minimum of approximately 12 and up to approximately 18 patients for Part II are expected. Fewer or more patients might be needed based on the recommendation of the SMC and the actual number of cohorts tested.

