Operating characteristics are a way to assess the long-run behaviour of a model by illustrating the precision of the design in estimating the MTD. Under an assumed true dose-toxicity curve, metrics such as the probability of recommending a dose with true DLT rate in the target interval can be approximated via simulation. Table 10.5: 5 describes 4 assumed true dose-toxicity scenarios which were used to assess the operating characteristics of the model. These scenarios reflect a wide range of possible cases as follows:

- Scenario 1: aligned with prior means
- Scenario 2: low-toxicity scenario
- Scenario 3: high-toxicity scenario
- Scenario 4: low-toxicity followed by high-toxicity

Table 10.5: 5 Assumed true dose-toxicity scenarios

Scenario		BI 754091 / BI 754111 (mg / mg)			
		240 / 200	240 / 400	240 / 600	240 / 800
1: Prior	P(DLT)	0.146	0.175	0.198	0.214
2: Low Tox		0.001	0.009	0.028	0.160
3: High Tox		0.100	0.200	0.300	0.600
4: Low-High		0.001	0.180	0.360	0.720

Proprietary confidential information © 2021 Boehringer Ingelheim International GmbH or one or more of its affiliated companies

For each of these scenarios, 1000 trials were simulated. The each cohort consisted of 3 patients and the MTD was considered reached if at least 6 patients have been evaluated at a dose level which is the model's recommendation for the next dose cohort and for which the posterior probability of targeted toxicity was at least 50%.

It was then assessed how often a dose was declared as MTD with true DLT rate in the under-, targeted-, or over-dose range. Furthermore, the average, minimum and maximum number of patients per trial and the average number of DLTs per trial are reported. Results are shown in Table 10.5: 6.

Table 10.5: 6 Simulated operating characteristics

Scenario	% of trials declaring a MTD with true DLT rate in				# Patients	# DLTs
	Underdose	Target dose	Overdose	Stopped Before MTD	Mean (Min-Max)	Mean (Min-Max)
1: Prior	14.0	69.3	0	16.7	27.41 (9-60)	1.24 (0-4)
2: Low Tox	21.0	72.8	0	6.2	11.97 (3-42)	2.161 (1-7)
3: High Tox	8.6	75.4	1.5	14.5	11.5 (3-30)	2.5 (1-9)
4: Low-High	5.5	66.9	18.2	9.4	11.7 (3-42)	2.57 (1-9)

In scenario 1 (Prior), which reflects the case that the true dose-toxicity is aligned with prior means, 69.3% of the simulated trials that have found a MTD declared the MTD with true toxicity rate in the target interval.

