In scenario 2 (Low-toxicity scenario), almost all simulated trials (93.8%) are declared as MTD in underdose or target dose. The result is similar to scenario 1.

In scenario 3 (High-toxicity scenario), 75.4 % of the simulated trials are declared to MTD with true toxicity rate in the target intervals. Though overdose toxicity is assumed but the only 1.5% is declared as MTD in overdose.

In scenario 4 (Low-High scenario) shows 66.9% of the simulated trials declared a dose as MTD with true DLT rate in the targeted dose range. 18.2% of the simulated trials declared a dose as MTD in the overdose range. This is because the assumed true dose-toxicity rate at 240/600 mg and 240/800 mg was above 33%.

The mean patients numbers range is from 3 to 60 patients and the DLT numbers range is from 0 to 9.

In summary, the considered data scenarios show a reasonable behaviour of the model and the operating characteristics demonstrate a good precision of MTD determination.

10.6 iRECIST

Immunotherapeutics may result in infiltration of immune cells leading to transient increase in the size in malignant lesions, or undetectable lesions becoming detectable. The criteria are identical to those of RECIST 1.1 in many respects but have been adapted to account for instances where an increase in tumour burden, or the appearance of new lesions, does not reflect true tumour progression. Key differences are described below. All responses defined using iRECIST criteria are designated with a prefix. iRECIST time-point and best overall responses will be recorded separately.

Confirming progression

Unlike RECIST 1.1, iRECIST requires the confirmation of progression and uses the terms iUPD (unconfirmed progression) and iCPD (confirmed progression). Confirmatory scans should be performed at least 4 weeks, but no longer than 8 weeks after iUPD.

iCPD is confirmed if further increase in tumour burden, compared to the last assessment, is seen as evidenced by one or more of the following:

- Continued increase in tumour burden (from iUPD) where RECIST 1.1 definitions of progression had been met (from nadir) in target, non-target disease or new lesions
 - Progression in target disease worsens with an increase of at least 5 mm in the absolute value of the sum
 - Continued unequivocal progression in non-target disease with an increase in tumour burden

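### Rows 1 (Prior) and 2 (Low Tox) of Table 10.5: 6 contradict the DLT rates they were simulated from, and were probably exchanged

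*Protocol*

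**What the plan says.** A Part II primary endpoint is the "MTD of the BI 754091 plus BI 754111 combination" (Protocol 2.1.2). Appendix 10.5 presents the simulated performance of the dose-finding model for that endpoint, with 1000 trials per scenario.

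Table 10.5: 5 gives the assumed true DLT rates at 240 mg BI 754091 plus 200, 400, 600 and 800 mg BI 754111. Prior uses 0.146, 0.175, 0.198 and 0.214. The second row reads "2: Low Tox 0.001 0.009 0.028 0.160".

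Table 10.5: 6 reports:

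| Row as labelled | Underdose % | Target % | Overdose % | Stopped % | Mean patients (range) | Mean DLTs (range) |
|---|---|---|---|---|---|---|
| 1: Prior | 14.0 | 69.3 | 0 | 16.7 | 27.41 (9-60) | 1.24 (0-4) |
| 2: Low Tox | 21.0 | 72.8 | 0 | 6.2 | 11.97 (3-42) | 2.161 (1-7) |

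The narrative attributes 69.3% to scenario 1. For scenario 2 it says "In scenario 2 (Low-toxicity scenario), almost all simulated trials (93.8%) are declared as MTD in underdose or target dose" and describes the result as close to that of scenario 1. It concludes that "the operating characteristics demonstrate a good precision of MTD determination".

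On dose range, Section 1.4 says that "dose levels which are higher than the ones investigated in preceding trials 1381-0001 and 1381-0002 will not be investigated in this trial". Section 4.1.2.2 reports, from a mid-2018 data cut of 1381-0002, that "BI 754111 was administered at dose range from 4 mg to 600 mg in combination with BI 754091 240 mg". Table 4.1.3: 2 lists 800 mg as a provisional level, with actual assignments decided by the SMC.

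**The concern.** The row labelled as the low-toxicity scenario shows more DLTs in fewer patients than the row labelled Prior. Yet its assumed rates are far lower at 200 to 600 mg and lower at 800 mg too. That ordering suggests mislabelled results.

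Low Tox is also the scenario a reader will look to first. Trial 1381-0002 had no DLT in 48 evaluable patients (Table 4.1.2.2: 1), so of the four curves this one is closest to the data. As printed, it looks as if about 12 patients suffice to declare an MTD, nearly always. If the figures belong to another scenario, the protocol misdescribes how its Part II design behaves in the most plausible case. In that scenario, correct selection also depends wholly on one dose level whose availability is conditional.

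**Working it through.** **The plan's own figure.** 21.0 + 72.8 = 93.8, so the narrative's scenario 2 figure is the sum of the printed Low Tox entries. Both rows add to 100: 14.0 + 69.3 + 0 + 16.7 and 21.0 + 72.8 + 0 + 6.2.

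**Bound.** Each simulated patient has a DLT with the true rate of the dose received. So mean DLTs = Σ (mean patients at dose d × rate at d), and the patient means add up to mean N. Therefore

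mean N × lowest rate ≤ mean DLTs ≤ mean N × highest rate.

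This holds whatever the prior, the dose assignment or the stopping rule.

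| Row as labelled | Lower bound | Upper bound | Printed | Feasible? |
|---|---|---|---|---|
| Prior | 27.41 × 0.146 = 4.00 | 27.41 × 0.214 = 5.87 | 1.24 | No |
| Low Tox | 11.97 × 0.001 = 0.01 | 11.97 × 0.160 = 1.92 | 2.161 | No |
| High Tox | 11.5 × 0.100 = 1.15 | 11.5 × 0.600 = 6.90 | 2.5 | Yes |
| Low-High | 11.7 × 0.001 = 0.01 | 11.7 × 0.720 = 8.42 | 2.57 | Yes |

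If the simulation starts at 400 mg, as the trial does, with cohorts of 3, the Low Tox ceiling falls to 3 × 0.009 + 8.97 × 0.160 = 1.46.

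**Could simulation error explain it?** With 1000 trials, SE = √(N × p × (1 − p) / 1000).

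- Low Tox: √(11.97 × 0.160 × 0.840 / 1000) = 0.040. The excess is 2.161 − 1.915 = 0.246, about 6 SE.
- Prior: √(27.41 × 0.146 × 0.854 / 1000) = 0.058. The shortfall is 4.00 − 1.24 = 2.76, about 47 SE.

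It cannot.

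**Exchange the two rows.**

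- Prior rates with 11.97 patients: 11.97 × 0.146 = 1.75 to 11.97 × 0.214 = 2.56. The value 2.161 fits.
- Low Tox rates with 27.41 patients: 27.41 × 0.001 = 0.03 to 27.41 × 0.160 = 4.39. The value 1.24 fits.

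**Pattern in Part I.** Table 10.5: 3 passes the same bound in all four rows. Its Low Tox row shows 34.8 patients (6-60) and 0.8 DLTs (0-2), and the text notes that "The mean patients number was around 35 patients at scenario 2". It is the only Part I row that reaches 60 patients or contains a trial without a DLT. The others have maxima of 30 to 33 patients and a minimum of 1 DLT. In Part II those features (9-60 patients, 0-4 DLTs) sit in the row labelled Prior.

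**Percentages.** The bound says nothing about these columns. Neither scenario has a dose at or above 0.33, so the printed 0% overdose fits both and cannot tell them apart. If the whole rows were exchanged, Low Tox is 14.0% underdose, 69.3% target, 16.7% stopped, and 14.0 + 69.3 = 83.3% declared rather than 93.8%. Prior is 21.0%, 72.8% and 6.2%.

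**Where the target doses are.** The target interval is [0.16, 0.33). Of the Low Tox rates 0.001, 0.009, 0.028 and 0.160, only the last lies in it. Every target-dose declaration in that scenario is therefore at 800 mg, whichever row is correct.

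**The case against.** The case for leaving this alone is that it is a transcription slip in an appendix with little consequence. Much of that stands.

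- Exchanging whole rows moves Low Tox target selection only from 72.8% to 69.3%. The range over the four scenarios stays at 66.9% to 75.4%.
- The SAP (7.4) derives the MTD from the fitted model and the observed DLTs, not from this table.
- Part III had been recruiting since before December 2019 (Section 3.1), so current dosing is unaffected.
- The Part I comparison concerns monotherapy with a two-parameter model and another prior. It supports the pattern only.

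On the dose limit, a reader might infer that 800 mg is closed, so that Part II had no chance of declaring a target-range MTD under low toxicity. The documents do not support that. The 600 mg figure is a June 2018 data cut from a trial then ongoing. Section 1.4 ties the limit to whatever that trial investigates, and the Amendment 1 rationale foresees that a higher dose tested there could be used here. Zero selection when no open dose is in the interval would also be true by definition, not a design failure. The protocol already allows for this outcome: dose finding may end by confirming the RD from 1381-0002 (3.1, 4.1.8), the SMC may declare an RD independently of the MTD estimate (3.1), and other data including PK are used if DLTs are too few (5.2).

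A reader might also set 27.41 patients against Section 7.7.1, "A minimum of approximately 12 and up to approximately 18 patients for Part II are expected", and infer an overrun. That does not follow. The simulation required both 6 patients at the dose and at least 50% posterior target probability, whereas the trial needs only one of its two criteria (4.1.6, 7.1.2). Section 7.7.1 also allows for fewer or more patients.

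None of this rescues the two rows. They contradict Table 10.5: 5 on any reading.

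**Conclusion.** The point holds as a minor correction of stated operating characteristics. That the patient and DLT means in rows 1 and 2 are wrong as labelled follows from printed figures alone, by about 6 and 47 simulation standard errors. It assumes only that Table 10.5: 5 lists the rates actually used.

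That the two rows were exchanged is a strong inference: it repairs both rows and matches the Part I low-toxicity pattern of many patients and few DLTs. That the percentages moved with them is likely but unproven. It would therefore go too far to state that 69.3% and 93.8% are misassigned before the output has been checked.

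Separately, the general claim of good precision needs a qualification for Low Tox. There, correct selection rests entirely on 800 mg, and the documents do not say whether that dose became available.

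**What to change.** 1. Check the archived simulation output for Part II scenarios 1 and 2, including the percentage columns.
2. Correct rows 1 and 2 of Table 10.5: 6 and the matching narrative: the 69.3% for scenario 1, and the 93.8% and the comparison with scenario 1 for scenario 2. If whole rows were exchanged, these become 72.8% for scenario 1 and 83.3% for scenario 2, with a Low Tox mean of 27.41 patients. State that this mean applies under the simulated stopping rule, which requires both conditions.
3. Add a note that under Low Tox only 800 mg lies in the target interval, so target-dose declarations there depend on 800 mg being open under the Section 1.4 limit. Qualify the closing statement on precision for that scenario.

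The cost is a look-up, two table rows and a few sentences. If the output was not kept, two scenarios must be re-run. No patients, visits or data are added.
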